APPENDIX 1. LIVER TISSUE BIOPSY, BILE DUCT SPECIMEN, & SCORING PROTOCOL

Liver Parenchyma Tissue Sample:

- Each tissue specimen is a 2.0 cm long 16-gauge needle biopsy taken perpendicular to the liver capsule from the right lobe. It should be stressed that the needle NOT be inserted parallel to the capsule.
- The tissue sample can then be placed in 10% neutral-buffered formalin, which is standard at most institutions.
- The specimen container must be CLEARLY LABELED with an anonymous code and specimen information. Bar coding is preferable.
- The label should also contain the timing of the biopsy: a) donor pre-retrieval; b) post-preservation (before implant); and c) post-reperfusion.

Timing of Liver Biopsy Samples:

- Liver tissue samples taken at the following time points:
 - Donor liver pre-retrieval. Only donor livers that are clinically suspected to be fatty by retrieval team visualization, will require a pre-retrieval biopsy readout to estimate the degree of macrosteatosis and confirm eligibility ($\leq 40\%$ macrosteatosis)
 - Post-OCS and Control preservation at the end of back preparation and immediately before the start of re-implantation
 - 90-120 minutes after reperfusion of the transplanted liver (prior to abdominal closure)

Bile Duct Specimens (if applicable):

- Any tissue trimmed from the bile duct or cystic duct should be placed into 10% neutral buffered formalin, as above, and CLEARLY LABELED, as to the center and participant and location of the sample. For example, 001-001 "distal common bile duct trimming."

Timing of Bile Duct Specimen:

- Pathology sample of common bile duct taken post preservation (applies to both OCS and control arms).
 - Post preservation at the end of back preparation and immediately before the start of re-implantation OR
 - Post reperfusion-Prior to biliary anastomosis

Refer to core lab collection manual in the PROTECT Study Manual

Score

PARENCHYMAL CHANGES:

Total biopsy length: _____ mm Total number of portal tracts: _____ Biopsy Adequate: Yes No

Overall architectural integrity: normal/intact mild moderate severe distortion

1. Lobular necrosis:

1.1 Overall severity:	 NONE	 MILD	 MOD	 SEV	 N/A
1.2 Primary location:	 Periportal	 Midzonal	 Perivenular	 Panlobular	 NA
1.3 Secondary location	 Periportal	 Midzonal	 Perivenular	 Panlobular	 NA
1.4 Tertiary location:	 Periportal	 Midzonal	 Perivenular	 Panlobular	 NA

2. Lobular inflammation:

2.1 Overall severity:	 NONE	 MILD	 MOD	 SEV	 N/A
2.2 Primary location:	 Periportal	 Midzonal	 Perivenular	 Panlobular	 NA
2.3 Secondary location:	 Periportal	 Midzonal	 Perivenular	 Panlobular	 NA

3. Lobular inflammation type:

3.1 Primary type:	 Neutrophils	 Eosinophils	 Macrophage/monocyte	 Lymphocytes	 Plasma cells
3.2 Secondary type:	 Neutrophils	 Eosinophils	 Macrophage/monocyte	 Lymphocytes	 Plasma cells
3.3 Tertiary type:	 Neutrophils	 Eosinophils	 Macrophages/monocytes	 Lymphocytes	 Plasma cells

4. Lobular Steatosis:

4.1 Overall severity:	 NONE	 MILD	 MOD	 SEV	 N/A
4.2 Predominant distribution:	 Periportal	 Midzonal	 Perivenular	 Panlobular	 NA

5. Liver Sinusoidal Endothelial Cell (LSEC) integrity/coverage (based on CD31 staining)

5.1 Overall percentage of sinusoids covered _____ (nearest 10%)	 Periportal	 Midzonal	 Perivenular	 Panlobular	 NA
5.2 Primary LSEC loss:	 Periportal	 Midzonal	 Perivenular	 Panlobular	 NA
5.3 Secondary LSEC loss:	 Periportal	 Midzonal	 Perivenular	 Panlobular	 NA

EXTRA-HEPATIC BILE DUCT CHANGES:(adapted from Hansen et al *Virchows Arch* 2012;461:41-48; and op den Dries *J Hepatol.* 2014 Jun;60(6):1172-9):

1. Surface epithelial loss: 0: no loss 1: ≤ 50% > 50%
2. Bleeding: 0: no bleeding 1: ≤ 50% > 50%
3. Thrombi: 0: no thrombi 1: thrombi present
4. Vascular lesions: 0: no lesions 1: ≤ 50% vessels > 50% vessels
5. Arteriolonecrosis: 0: no lesions 1: ≤ 50% vessels > 50% vessels
6. Duct necrosis: 0: no lesions 1: <25% 2: 25-50% 3: 50-75% > 75% necrosis
7. Inflammation: 0: none; 1: at least > 10 leukocytes/HPF; 2: >50/HPF
8. Subluminal gland injury: 0: no injury 1: ≤ 50% > 50%
9. Deep gland injury: 0: no loss 1: ≤ 50% > 50%

APPENDIX 2. SCHEDULE OF CLINICAL ASSESSMENTS

Evaluations	Donor & Liver Assessments	
	OCS Preservation	Cold Flush and Storage (Control)
Eligibility & ID	X	X
Demographics/Characteristics	X	X
Donor Cause of Death	X	X
Donor Medical & Social History	X	X
Donor Liver Assessment	X	X
Donor Cross Clamp Time and Flush Detail	X	X
Post-Preservation Liver Biopsy and if applicable Bile duct specimen	X	X
OCS Preservation Parameters	X	
OCS Liver Enzymes & Lactate Levels	X	
Device Malfunction (if applicable)	X	
Non-transplant Reasons (if applicable)	X	X

Evaluations	Recipient Schedule of Assessments					
	Tx. Day -Day 7 Post-Tx.	Discharge	Day 30	Month 6	Month 12	Month 24
Eligibility & Informed Consent	X					
Randomization	X					
Demographic/Characteristics	X					
Medical & Risk Factors	X					
Transplant Details	X					
Early Liver Allograft Dysfunction (EAD) Surveillance	X					
Mechanical Ventilator Support	X					
Patient Survival	X	X	X	X	X	X
Graft Survival	X	X	X	X	X	X
Immunosuppressive Meds & Induction (if applicable)	X	X				
Initial ICU & Hospital Stay	X	X				
Liver Graft-Related (AE's & SAE's)	X	X	X			
Liver Biopsy *	X				X	X

* ONLY Tests regularly scheduled per center standard of care or performed due to a clinical cause at these time-points will be collected.

**APPENDIX 3. DRAFT PATIENT INFORMED CONSENT FORM
TEMPLATE**

(This Page is Intentionally Left Clear)

APPENDIX 4. DRAFT ELECTRONIC CASE REPORT FORMS

(This Page is Intentionally Left Clear)

4.1.3	Non-Ischemic Biliary Complications within 30 Days and 6 Months Post-Transplant (Per Protocol Population)

Table	Title
4.1.4	Non-Ischemic Biliary Complications within 30 Days and 6 Months Post-Transplant (mITT Population)
4.1.5	Non-Ischemic Biliary Complications within 30 Days and 6 Months Post-Transplant (As Treated Population)
4.1.6	Exploratory Safety Endpoint of Non-Ischemic Biliary Complications within 30 Days Post-Transplant (As Treated Population)

List of Figures

Figure	Title
2.1.1	Kaplan-Meier Estimated Recipient Survival Time Probabilities (Per Protocol Population)
2.1.2	Kaplan-Meier Estimated Liver Graft Survival Time Probabilities (Per Protocol Population)
3.1.1	Kaplan-Meier Estimated Cumulative Distribution Function of Time to Any Post-Treatment Serious Adverse Event (As Treated Population)

List of Abbreviations

Term	Definition
AE	Adverse Event
ALT	Alanine Aminotransferase
AST	Aspartate Aminotransferase
AT	As Treated Population
BMI	Body Mass Index
CEC	Clinical Events Committee
CI	Confidence Interval
CRF	Case Report Form
CSR	Clinical Study Report
DBD	Donor after Brain Death
DCD	Donor after Circulatory Death
EAD	Early liver Allograft Dysfunction
GGT	Gamma-Glutamyl Transferase
ICU	Intensive Care Unit
INR	International Normalized Ratio
IWRS	Interactive Web Response System
LLT	Lowest Level Term
LGRSAE	Lung Graft Related Serious Adverse Event
MAR	Missing at Random
MedDRA	Medical Dictionary for Regulatory Activities
MELD	Model for End-Stage Liver Disease
MI	Multiple Imputation
mITT	Modified Intent-to-Treat Population
OCS	Organ Care System
PP	Per-Protocol Population
SAE	Serious Adverse Event
SAP	Statistical Analysis Plan
SOC	Standard of Care
TEAE	Treatment-Emergent Adverse Event

1. INTRODUCTION

Descriptions of planned analyses are provided in order to avoid post hoc decisions that may affect the interpretation of the statistical analysis. The statistical methods applied in the design and planned analyses of this study are consistent with the International Conference on Harmonisation (ICH) guideline *Statistical Principles for Clinical Trials* (1998).

This Statistical Analysis Plan (SAP) will be finalized prior to data analysis (and before database lock). Any changes between the statistical methods provided in the clinical study protocol and this SAP will be explained herein; any changes or deviations from this SAP relative to the final analysis will be fully documented in the CSR.

2. STUDY OBJECTIVE

The objective of this trial is to compare the safety and effectiveness of the OCS™ Liver (OCS) vs. standard cold storage (Control) to preserve and assess donor livers having one or more of the following characteristics:

- Donor age \geq 40 years old
- Expected cross clamp time \geq 6 hours
- Donor after circulatory death (DCD) with age \leq 55 years old
- Steatotic liver $>0\%$ and $\leq 40\%$ macrosteatosis at time of retrieval (based on retrieval biopsy readout only if the donor liver was clinically suspected to be fatty by the retrieval surgeon at time of liver retrieval)

3. STUDY DESIGN

3.1. Overview

This study is a prospective, multi-center, randomized, controlled Phased Pivotal trial with transplanted recipients assigned to either the OCS Liver arm (OCS - treatment) or standard of care cold storage arm (SOC - control). The trial will have two parts (Part A rolling into large Part B, assuming stopping rule is not triggered):

- Part A: Include the first 20 randomized transplanted liver recipients with pre-specified stopping rule to ensure safety.
- Part B: assuming no stopping rule was triggered, the trial enrollment will continue beyond the initial 20 transplanted recipients in Part A into Part B, while the data from the first 20 subjects are being reviewed. All of the final analyses of the study will be based on the pooled data from Parts A and B.

This trial will be conducted at no more than 25 institutions in the United States and worldwide (Europe, Australia and Canada) and will include up to 300 transplanted Liver recipients. The number of subjects was determined as described in Section 3.4 of this statistical analysis plan. All subjects will be followed for a minimum of 30 days post-transplant. Patients will be followed for a maximum of 24 months from the date of transplantation. The summary of the follow-up is as follows:

- All subjects will be followed from transplant to discharge
- Thirty-day patient and graft survival will be documented on Day 30 post-transplant eCRF
- 6, 12, and 24 months patient follow-up.

3.2. Method of Assigning Subjects to Treatment

After confirmation of eligibility, obtaining informed consent, and a matching donor liver is identified, potential liver transplant recipients will be randomized 1:1 to have their donor livers preserved using either the OCS Liver perfusion or the standard cold storage preservation technique using cold flush and storage. Randomization will be performed through the Interactive Web Response System (IWRS). Subjects who are not transplanted with the matching donor liver will be re-randomized and treated as a new subjects without any randomization assignment.

3.3. Blinding

Not applicable.

3.4. Determination of Sample Size

The sample size for this trial was determined based on the primary effectiveness endpoint, Early Liver Allograft Dysfunction (EAD) in the first 7 days post-transplantation. The sample size calculation assumed a one-sided, normal approximation test for non-inferiority, an alpha level of 0.05, a non-inferiority margin of 0.075, a 1:1 allocation, true proportions for the primary effectiveness endpoint of 0.2 for the OCS treatment and 0.25 for the Control treatment, and power of 80%. Based on these specifications, the required sample size was determined to be 144 transplanted recipients per treatment group, or 288 total transplanted subjects. To ensure an

adequate number of subjects in the Per Protocol Population, the sample size was increased to a total of 300 transplanted subjects. Subjects will be enrolled until there are either 290 subjects in the Per Protocol Population or a total of 300 transplanted subjects, whichever comes first.

3.5. Changes to the Protocol-Specified Analyses

The sample size re-estimation proposed in the protocol will not be performed per FDA recommendation. Enrollment will be concluded at the original planned sample size of 300 patients as FDA has recommended ([REDACTED]).

As recommended by FDA, additional post-hoc exploratory analyses for the primary endpoint have been added to test for site poolability, with small sites pooled by US geographic region. ([REDACTED]).

Post-hoc tipping point sensitivity analyses have been added based on FDA's recommendation for the primary efficacy endpoint and the two secondary efficacy endpoints ([REDACTED]).

Two exploratory study populations have been added to the analyses. The exploratory mITT2 population will include an additional 43 subjects who have been transplanted off-study with a randomized organ, and the exploratory ITT population will include all subjects who have signed informed consent, been enrolled in the study, randomized, and the assigned liver preservation method has been initiated. An Exploratory analysis will be included for the mITT2 and ITT populations of patient and graft survival at 30 days post-transplant. ([REDACTED]).

Analyses of the primary effectiveness endpoints and secondary effectiveness endpoints by donor inclusion criteria will be performed.

The incidence of non-ischemic biliary complications in 30 days and in 6 months, defined using MedDRA terminology, will be reported ([REDACTED]).

Subgroup reporting has been added for Donor after Brain Death (DBD) transplants. The two subgroups used in recipient reporting are DBD transplants with total cross clamp time \geq 6 hours and DBD transplants with total cross clamp time $<$ 6 hours ([REDACTED]).

4. EFFECTIVENESS AND SAFETY ENDPOINTS

4.1. Primary Effectiveness Endpoint

Incidence of Early liver Allograft Dysfunction (EAD) or primary non-function, defined as presence of one or more of the following criteria:

- AST level > 2000 IU/ml within the first 7 postoperative days
- Bilirubin \geq 10 mg/dl on postoperative Day 7
- INR \geq 1.6 on postoperative Day 7
- Primary non-functioning graft within the first 7 days (defined as irreversible graft dysfunction requiring emergency liver re-transplantation or resulting in death, in the absence of immunologic or surgical causes)

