Primary Effectiveness Endpoint	
Incidence of Early liver Allograft Dysfunction (EAD) or primary non-function, defined as presence of one or more of the following criteria:
 
 • AST level >2000 IU/ml within the first 7 postoperative days; • Bilirubin ≥ 10 mg/dl on postoperative day 7; • INR ≥ 1.6 on postoperative day 7; or • Primary non-functioning graft within the first 7 days (defined as irreversible graft dysfunction requiring emergency liver re-transplantation or death, in the absence of immunologic or surgical causes)
Secondary Effectiveness and OCS Donor Liver Assessment Endpoints	
 • OCS donor liver assessment during perfusion, defined as, among donor livers preserved using OCS for the entire preservation period, the proportion of livers on which measurements of all of the following during perfusion will be available on OCS device before transplant 
 ◦ Lactate level (every two hours) ◦ Average bile production rate (based on total bile production volume and duration of OCS perfusion) ◦ Hepatic Artery Pressure (continuously) ◦ Portal Vein Pressure (continuously) • Patient survival at day-30 post-transplantation • Patient survival at initial hospital discharge post liver transplantation
Other Endpoints	
 • Length of initial post-transplant ICU stay • Length of initial post-transplant hospital stay • Evidence of ischemic biliary complications diagnosed at 6 and at 12 months • Extent of reperfusion syndrome as assessed based on the rate of decrease of lactate over the following time points: 
 ◦ During anhepatic phase immediately before reperfusion of the transplanted liver ◦ 30-40 minutes after hepatic artery and portal vein reperfusion of the transplanted liver ◦ 90-120 minutes after reperfusion of the transplanted liver • Pathology sample score for liver tissue samples taken at the following time points (applies to both OCS and Control arms): 
 ◦ Donor liver pre-retrieval ◦ Post-OCS and Control preservation at the end of back preparation and immediately before the start of re-implantation ◦ Post reperfusion 90-120 after reperfusion of the transplanted liver

	(prior to abdominal closure)

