 - Methylprednisolone steroid
 - NaHCO₃ for buffer
 - Heparin
 - Vitamins and trace elements
 - Prostacyclin for vasodilatation
 - Calcium chloride
 - Taurocholic acid for bile salts
 - Parenteral nutrition solution supplemented with amino acids
 - Insulin

Figure 3:

[figure not shown]

Fig. 3 . Markers of liver injury and function (n=5) during extracorporeal liver perfusion. (A) ALT (serum glutamic pyruvic transaminase) levels (normal porcine range 31–58 U/L) and alkaline phosphatase levels (normal porcine range 180–813 U/L). (B) Bile output measured as ml of bile produced per hour and total bilirubin expressed in $\mu\text{mol/L}$. (normal porcine range up to 0–17.1 $\mu\text{mol/L}$). (C) Oxygen consumption calculated by the Fick equation and expressed as ml O_2 /min/liver.

- In 2009, Brochman J., et al.⁷ reported the successful preservation of heart beating and DCD swine livers using blood based, normothermic ex-vivo machine perfusion for up-to 20 hours and subsequent transplantation. This study demonstrated a clear trend towards better liver function in the normothermic perfusion groups as compared to cold storage for both heart beating and DCD livers. In addition, this report suggested that bile production; AST levels and portal vein pressure as potential ex-vivo perfusion predictors for post-transplant viability in pigs. The perfusate mix used for this study consisted of:
 - Swine whole blood
 - Colloid solution
 - Antibiotics
 - Methylprednisolone steroid
 - NaHCO_3 for buffer
 - Heparin
 - Vitamins and trace elements
 - Prostacyclin for vasodilatation
 - Calcium chloride
 - Taurocholic acid for bile salts
 - Parenteral nutrition solution supplemented with amino acids
 - Insulin
- In 2011, Fondevila, et al.⁸ reported successful transplantation of swine DCD livers after 90 minutes of cardiac arrest by using ex-vivo normothermic blood based perfusion (NMP) of donor swine livers. This report demonstrated that when normothermic ex-vivo perfusion was used it resulted in 100% survival of the swine post-transplantation as compared to 83% when in-vivo NMP was used and 0% when cold storage was used. This report demonstrated good histological pictures of all

livers perfused using ex-vivo normothermic blood based perfusion. The perfusate mix used for this study consisted of:

- Swine whole blood
- NaHCO₃ for buffer
- Heparin

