Primary non-function rate	0 (0)	0 (0)
Early Allograft Dysfunction, n (%)	3 (15%)	9 (22.5%)
Peak AST within 7 days, (IU/L), median (range)	417 (84-4681)	902 (218-8786)
Initial Post-Tx. ICU stay (days), median (range)	3 (1-8)	3 (1-41)
Hospital Stay (days), median (range)	12 (6-34)	14 (8-88)

[figure not shown]
Source: Rising Star Symposium, International Liver Transplant Society, June 5, 2014, London, England; Abstract O-1, Human Liver Transplantation Using Normothermic Machine Preservation, Friend P, et al.
Sunrise Symposia; New Dimensions in Liver Transplantation, World Transplant Congress, July 31, 2014, San Francisco, CA, U.S.A.; Normothermic Machine Preservation of the Liver, Friend P, et al.

Based on the above overwhelming supportive pre-clinical, scientific and clinical evidence of safety, feasibility and potential benefits of warm machine perfusion for liver transplantation using identical perfusion protocols/perfusates to the OCS liver technology, we are proposing to proceed with a pivotal prospective clinical investigation of the OCS liver technology to compare its outcomes to cold static storage in liver transplant recipients.

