4. TRIAL ENDPOINTS

4.1. Primary Effectiveness Endpoint

Incidence of Early liver Allograft Dysfunction (EAD) or primary non-function, defined as presence of one or more of the following criteria:

- AST level>2000 IU/ml within the first 7 postoperative days;
- Bilirubin ≥ 10 mg/dl on postoperative day 7;
- INR ≥ 1.6 on postoperative day 7; or
- Primary non-functioning graft within the first 7 days

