14.9. Medical Monitor

The Sponsor will utilize an independent Medical Monitor to provide individual serious adverse event adjudication for the trial. It is anticipated that the Medical Monitor will meet with the Sponsor on a periodic basis, or as needed, depending on the rate of patient accrual. The primary responsibilities of the Medical Monitor are to:

- Review serious adverse events that occur over the course of the trial and the subsequent classification of these adverse events as related to the device
- Review donor and recipient treatment group eligibility issues.
- Evaluate possible protocol deviations.
- Provide oversight for issues affecting general patient welfare.
- Provide recommendations to extend the length of follow-up past 30 days post-transplant for a subject experiencing a serious adverse event.
- Review all site reported EAD diagnosis based on the pre-specified protocol criteria and actual clinical case of the trial patient.

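### The AST criterion of the primary effectiveness endpoint is written per millilitre in all seven statements, while the documents' readable AST data are per litre; as written, that one component could not be met

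*SAP*

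**What the plan says.** EAD is the only primary effectiveness endpoint, and meeting any one of four criteria makes an event: AST, bilirubin on Day 7, INR on Day 7, or primary non-function within 7 days.

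The AST criterion appears seven times, with the same unit each time:

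- SAP 4.1 and SAP 12.1: "AST level > 2000 IU/ml within the first 7 postoperative days"
- Protocol synopsis (primary endpoint row and effectiveness analysis row), Protocol 7.2 and Protocol 9.3.1: "AST level >2000 IU/ml within the first 7 postoperative days"
- Protocol 4.1: "AST level>2000 IU/ml within the first 7 postoperative days"

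No section states the threshold per litre or gives a conversion. The enzyme values that can be read in the documents are per litre. The feasibility table in Protocol 1.4.4 labels its row "Peak AST within 7 days, (IU/L), median (range", the same analyte over the same 7-day window. The Figure 3 caption in Protocol 1.4.2 gives a porcine ALT reference as "normal porcine range 31–58 U/L".

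Two other provisions bear on how the text would be used. Protocol 14.9 asks the Medical Monitor to "Review all site reported EAD diagnosis based on the pre-specified protocol criteria", and the sentence goes on to include the patient's actual clinical case. SAP 1 says that "any changes or deviations from this SAP relative to the final analysis will be fully documented in the CSR".

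**The concern.** A threshold in the primary endpoint definition decides who counts as an event, so its unit has to be right. Here it conflicts with the documents' own AST data by a factor of 1000. Because the protocol and the SAP carry the same unit, neither can be used to correct the other, and the list of changes in SAP 3.5 contains no unit correction.

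There are two ways forward from the current text. If programmers apply 2000 IU/L without comment, the result is what was presumably intended, but the primary analysis departs from its written definition. If they apply the text literally, one of the four criteria drops out, EAD rests on the other three, and the planning rates of 0.20 (OCS) and 0.25 (Control) no longer describe the endpoint being tested.

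**Working it through.** **1. The plan's sample size, for context.** Inputs from SAP 3.4: rates 0.20 and 0.25, margin 0.075, one-sided alpha 0.05, power 80%. The distance from the margin is 0.075 + 0.05 = 0.125, and the variance sum is 0.2×0.8 + 0.25×0.75 = 0.3475.

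- Normal approximation: n = (1.645 + 0.842)² × 0.3475 / 0.125² ≈ 138 per group. The Farrington-Manning score formula gives 140. The plan states 144.
- Power at 144 per group, normal approximation: Φ(0.125/√(0.3475/144) − 1.645) = 0.816.

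The stated size therefore delivers its 80% power at those rates. The unit question does not alter this calculation; it alters whether the rates describe the endpoint.

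**2. Unit conversion.** 2000 IU/ml × 1000 = 2,000,000 IU/L. Against the table in Protocol 1.4.4:

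| Peak AST within 7 days | IU/L | IU/ml | 2,000,000 ÷ value | Above 2000 IU/L? |
|---|---|---|---|---|
| Machine perfusion, median | 417 | 0.417 | 4,796 | no |
| Machine perfusion, maximum | 4,681 | 4.681 | 427 | yes |
| Cold storage, median | 902 | 0.902 | 2,217 | no |
| Cold storage, maximum | 8,786 | 8.786 | 228 | yes |

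Read per litre, the threshold lies inside both reported ranges (84–4,681 and 218–8,786). Read as written, it exceeds every value by more than two orders of magnitude.

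**3. What literal use would do to the non-inferiority test.** The share of EAD events that meet only the AST criterion is not in the documents, so the shares below are assumptions. If that share is s in an arm, the arm's rate becomes its intended rate × (1 − s). The test is the exact unconditional one ordered by the Farrington-Manning score, with 145 per arm (half of the 290 per-protocol target), margin 0.075 and critical z = −1.666 (maximum size 0.04998).

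True EAD by the intended definition exactly at the margin (OCS 0.325, Control 0.25), where any declaration is wrong:

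| AST-only share, OCS / Control | Literal rates, OCS / Control | P(non-inferiority declared) |
|---|---|---|
| 0 / 0 | 0.325 / 0.250 | 0.049 |
| 25% / 25% | 0.244 / 0.188 | 0.103 |
| 50% / 50% | 0.163 / 0.125 | 0.225 |
| 75% / 75% | 0.081 / 0.063 | 0.546 |
| 25% / 50% | 0.244 / 0.125 | 0.004 |

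True EAD at the planning rates (OCS 0.20, Control 0.25):

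| AST-only share, OCS / Control | Literal rates, OCS / Control | P(non-inferiority declared) |
|---|---|---|
| 0 / 0 | 0.200 / 0.250 | 0.814 |
| 25% / 25% | 0.150 / 0.188 | 0.813 |
| 50% / 50% | 0.100 / 0.125 | 0.840 |
| 75% / 75% | 0.050 / 0.063 | 0.924 |
| 25% / 40% (0.05 and 0.10 removed) | 0.150 / 0.150 | 0.547 |

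Equal shares shrink the difference between arms while the margin stays at 0.075, which helps OCS when the truth is at the margin. A larger AST-only share in Control removes more Control events and works against OCS. The second pattern cannot be dismissed: in Protocol 1.4.4 the median peak AST was 417 IU/L with machine perfusion and 902 IU/L with cold storage.

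**The case against.** The strongest reply is that this is an obvious unit slip. Laboratories and programmers would use IU/L, and the result would be what everyone intended. The recorded AST unit may also be fixed in the case report forms or the study manual, neither of which can be read here, and several AST figures are not shown, so the comparison rests on the readable values only. All of this stands, and it is why the point is minor in practice. It does not make the written definition correct, and a likely reading is not a pre-specified one.

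Three stronger readings are tempting, and the documents do not support them.

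- A reader might infer that the primary endpoint could never be met. Only the AST component is out of reach; the other three criteria still produce events.
- A reader might infer that literal use would make non-inferiority easier to declare. That follows at the margin with equal AST-only shares, but it reverses when the share is sufficiently larger in Control. The documents give no share for either arm, so the direction is unknown.
- A reader might take the Medical Monitor's review as enforcing the literal threshold. Protocol 14.9 also brings in the patient's actual clinical case, which makes mechanical use of 2,000,000 IU/L less plausible.

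**Conclusion.** The point holds as an internal inconsistency. The AST threshold is wrong as written in all seven statements: it equals 2,000,000 IU/L, 228 times the largest AST value readable in the documents. That the component could not be met is an inference from those values, but the gap is too wide for it to be in serious doubt.

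The likely practical effect is nil on the result, with an undocumented departure from the pre-specified text. The effect of literal use cannot be signed. Under the assumed shares, wrongful non-inferiority at the margin runs from 0.4% to 55%, against 4.9%. At the planning rates, the probability of declaring non-inferiority runs from 0.55 to 0.84 for shares up to 50%, against 0.81. These ranges show sensitivity to an unknown quantity and are not estimates of what would happen in this trial.

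**What to change.** 1. Confirm the unit in which AST is recorded in the case report forms and the laboratory data.
2. Before database lock, reconcile the threshold unit with it in SAP 4.1 and SAP 12.1 (IU/L fits the documents' own data), and add one line to SAP 3.5 recording the correction.
3. Correct the five protocol statements (synopsis twice, 4.1, 7.2 and 9.3.1) under the amendment policy in Protocol section 16. The sponsor must decide whether the correction qualifies as an administrative letter or needs an amendment, which would await IRB or ethics committee approval.

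The SAP change costs two edits and one added line. The protocol change carries the administrative cost of whichever route applies. Neither affects the data collected or the sample size.
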